#### Figure 3: Part A Weight-Tiered Dosing Regimens of Study Drug

\*In Part A, patients will receive dupilumab injections at the frequency of Q2W or Q4W with matching placebo alternating with dupilumab so the injection frequency will be identical within weight tiers for regimen-blinding purposes. Patients will remain within the originally assigned higher or lower dosing exposure arm throughout the study (Part A and Part B).

#### Figure 4: Part B Weight-Tiered Dosing Regimens of Study Drug

dupilumab so the injection frequency will be identical within weight tiers for regimen-blinding purposes. Patients will remain within the originally assigned higher or lower dosing exposure arm throughout the study (Part A and Part B).

## Figure 5: Part C (OLE) Weight-Tiered Dosing Regimens of Study Drug

# 8.2. Background Treatments

Patients who undergo a trial of PPI therapy prior to screening or during the screening period of Part A have the choice either to remain on the PPI regimen during Parts A and B or stop the PPI regimen prior to baseline; they then must remain off of PPIs during Parts A and B. Patients may adjust their PPI therapy use during Part C. Refer to the study binder for specific PPI dosing recommendations.

# 8.3. **Rescue Treatments and Procedures**

If medically necessary (eg, for treatment of intolerable EoE symptoms), rescue medications (systemic and/or swallowed topical corticosteroids) or emergency esophageal dilation are allowed for study patients. For Parts A and B, an endoscopy with biopsy will be performed prior to the initiation of rescue therapy. Patients who undergo an endoscopy with biopsy due to the initiation of rescue therapy during Parts A or B will not undergo the subsequent scheduled endoscopy/biopsy at week 16 and/or week 52, respectively. Patients who receive rescue treatment during the double-blind period of the study will not be eligible for the extended active treatment period unless an endoscopy with biopsy is performed prior to the initiation of rescue treatment is also allowed. If rescue therapy is initiated during Part C (OLE), an endoscopy/biopsy before initiating rescue treatment is at discretion of the investigator discretion; future endoscopies/biopsies (week 100 and week 160) would still be required. If the endoscopy with biopsies cannot occur due to COVID-19 restrictions, rescue treatment should be initiated without delay and these patients will be eligible to participate in Part C.

Regeneron Pharmaceuticals, Inc.

Patients receiving rescue therapy may continue to receive study drug. They will remain blinded and will be asked to return to the clinic for all remaining study visits for the double-blind treatment period and the follow-up period, and participate in all assessments for these visits according to the Schedule of Events specified in Table 1, Table 2, Table 3, and Table 4 except for endoscopy/biopsy, as noted above. For the purpose of efficacy analyses for Part A, patients who receive rescue treatment during the study will be considered treatment failures.

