#### Secondary Efficacy Endpoints for Part C (open-label extension period) only:

- Proportion of patients achieving peak esophageal intraepithelial eosinophil count of ≤6 eos/hpf (400×) at week 100 and week 160
- Proportion of patients achieving peak esophageal intraepithelial eosinophil count of <15 eos/hpf at week 100 and week 160
- Percent change in peak esophageal intraepithelial eosinophil count (eos/hpf) from baseline to week 100 and week 160
- Absolute change in mean EoE grade score from the EoE-HSS from baseline to week 100 and week 160
- Absolute change in mean EoE stage score from the EoE-HSS from baseline to week 100 and week 160
- Absolute change in EoE-EREFS from baseline to week 100 and week 160
- Normalized Enrichment Scores (NES) for the relative change from baseline to week 100 and 160 in the EoE diagnostic panel (EDP) transcriptome signature
- NES for the relative change from baseline to week 100 and week 160 in the type 2 inflammation transcriptome signature
- Change in total score from baseline to week 160 as measured by the PEESSv2.0caregiver version questionnaire
- Proportion of patients (with food elimination diet regimens at baseline) that have a reintroduction of a previously eliminated food group by week 100 and by week 160
- Change from baseline in body weight for age percentile up to week 160
- Change in body mass index for age z-score for patients ≥2 years of age from baseline to up to week 160
- Change in weight for age z-score from baseline to up to week 160
- Change in weight for height z-score from baseline to up to week 160

Regeneron Pharmaceuticals, Inc.

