#### CONFIDENTIAL

#### Figure 2: Endoscopy/Biopsy Procedure Flow Diagram

\* Biopsy specimens from the antrum and duodenum will be obtained in all patients to rule out alternate etiologies. All randomized patients found to have stomach and/or duodenal abnormalities at baseline will have follow-up stomach and/or duodenal biopsies at week 16, week 52, week 100, and week 160.

Patients who are on PPIs during the screening period to rule out EoE disease management with this treatment, and are eligible to enroll in the study, have the choice either to remain on the PPI regimen during the entire study or stop the PPI regimen prior to baseline; they then must remain off of PPIs during the entire study.

Biopsies will be obtained by endoscopy at the screening visit 2, week 16 visit, week 52, week 100 and week 160 visits, or immediately prior to start of rescue medication or procedures (only applies to rescue medication and/or procedures that occur before the week 52 visit). A total of at least 9 mucosal pinch biopsies will be collected at each time point from 3 esophageal regions: 3 proximal, 3 mid, and 3 distal. Two samples from each region will be used for histology (needed for study inclusion criteria, as well as endpoint assessment) and the others for RNA extraction. Biopsies will be used for exploratory research to study EoE, dupilumab mechanism of action, and to identify or validate predictive biomarkers (efficacy and/or safety). Exploratory analyses of the biopsies may include but are not limited to immunohistochemistry [IHC] and RNA sequencing (or other methods for assessing RNA expression and RNAscope).

Regeneron Pharmaceuticals, Inc.

CONFIDENTIAL

Patients may be re-screened if they fail the Part A baseline screening evaluation, unless the reason for screen failure is related to histologic inclusion criteria. The baseline endoscopy with biopsies and EoE-EREFS scoring will not be repeated for re-screened patients. These results will continue to be valid baseline data. Re-screening must occur within 6 months of the screen failure.

Patients may receive concomitant medications (except for prohibited medications specified in Section 8.10.1) as needed, at the discretion of the investigator, while continuing study treatment. Frequency of use and type of product will be documented.

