#### 8.10.1. Prohibited Medications and Procedures

Treatment with the following concomitant medications is prohibited through week 52 and may result in temporary or permanent discontinuation of study drug (see Section 8.4.2). While the investigator may suspend study treatment at any time, any change to study drug administration should be discussed with the medical monitor.

- Swallowed topical corticosteroids (may be used as rescue treatment for EoE) (Parts A and B only)
- Systemic corticosteroids (may be used as rescue treatment for EoE) (Parts A and B only)
  - NOTE: One-time use of a corticosteroid as a part of the anesthetic preparation used during each endoscopy procedure is also allowed.
- Systemic immunosuppressive/immunomodulating drugs (including, but not limited to, mepolizumab, omalizumab, cyclosporine, mycophenolate-mofetil, azathioprine, methotrexate, IFN-γ, or other immunomodulatory biologics)
- Treatment with an investigational drug (other than dupilumab)
- For Parts A and B: Initiation, discontinuation, or change in dosage regimen after baseline of the following medications (stable doses of these medications are allowed):
  - Proton pump inhibitors

- Systemic leukotriene inhibitors
- For Parts A and B: Initiation, discontinuation, or change in dosage regimen of nasal and/or inhaled corticosteroids within 8 weeks prior to visit 2, visit 8, or visit 17 endoscopies with biopsies
- Initiation of SCIT, or change in dose for those patients on a stable dose of SCIT, within 1 year prior to screening (For Parts A and B only)
- SLIT, OIT, or EPIT (For Parts A and B only)
- Treatment with a live (attenuated) vaccine, eg:
  - Chickenpox (varicella)
  - FluMist-influenza
  - Intranasal influenza
  - Measles (rubeola)
  - Measles-mumps-rubella combination
  - Measles-mumps-rubella-varicella combination
  - Mumps
  - Oral polio (Sabin)
  - Oral typhoid
  - Rubella
  - Smallpox (vaccinia)
  - Yellow fever
  - Bacille Calmette-Guerin
  - Rotavirus
  - Varicella zoster (shingles)

The following concomitant procedures are prohibited during study treatment (for Parts A and B):

- Major elective surgical procedures
- Esophageal dilation (may be used as rescue procedure)
- Initiation or change of food-elimination diet regimen

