#### 11.4.3. Efficacy Analyses

#### 11.4.3.1. Primary Efficacy Analysis

The primary analysis of proportion of patients achieving a histologic response of peak esophageal intraepithelial eosinophil count  $\leq 6 \text{ eos/hpf}$  at week 16 will be analyzed using the Cochran-Mantel-Haenszel (CMH) test to assess the difference in the proportion of responders in the FAS, adjusting for the randomization stratification factor (baseline weight group). The randomization stratification of baseline weight group may be pooled to ensure the sufficient sample size of each stratum.

For the primary estimands of interest for the primary endpoint, the intercurrent events, strategies, and the corresponding missing data handling approaches are provided as below:

	Estimands				
Endpoint Category	Endpoint(s)	Population	Intercurrent event(s) strategy and missing data handling	Population-level summary/Analysis	
Primary Endpoint	Proportion of patients achieving peak esophageal intraepithelial eosinophil count of ≤6 eos/hpf (400×) at week 16	FAS	
 
The intercurrent events will be handled as follows:
 
Treatment discontinuation: data collected after the patient discontinued treatment will be included in the analysis (Treatment policy strategy)
 
Initiation of treatment with systemic and/or swallowed topical corticosteroids drugs: patients will be considered as non-responders after such event (composite variable strategy)
 
Note: the composite strategy will be considered if a patient receives rescue medication any time during the study.
 
Missing data handling: patients with a missing value for the primary endpoint at week 16 due to study discontinuation or other reasons will be considered to be non-responders
 
	Cochran-Mantel-Haenszel (CMH) test adjusting for the randomization stratification factor (baseline weight group) will be utilized. The estimated proportion of the treatment difference between dupilumab groups and placebo, and its 2-sided 95% confidence intervals will be provided based on the CMH test.	

Sensitivity analyses will assess alternative methods to impute missing data. The sensitivity analyses will include tipping point analysis approach and worst observation carried forward – multiple imputation (WOCF-MI) approach.

Subgroup analyses (eg, by weight) may be performed. Details will be specified in the SAP.

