#### Efficacy Endpoints at Week 52 (Part B)

Efficacy endpoints at week 52 (Part B) will be analyzed descriptively at given visits for treatment received in Part B as well as by treatment group as in Part A (double-blind treatment period). No missing values will be imputed. These descriptive analyses may include statistical tests depending on the type of data in the same way as described above.

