#### Efficacy Endpoints (Part C)

Efficacy data in Part C will be summarized with descriptive statistics for treatment received in Part C as well as by treatment group as in Part A (double-blind treatment period) and Part B (extended active treatment period). No missing values will be imputed.

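### In Part C no rule makes rescue a non-response, so a remission reached on rescue steroids enters the week-100 and week-160 dupilumab response rates

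*Protocol*

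**What the plan says.** **Rescue rule.** Section 8.3 allows systemic or swallowed topical corticosteroids, or emergency dilation, as rescue. It then states: "For the purpose of efficacy analyses for Part A, patients who receive rescue treatment during the study will be considered treatment failures". In the estimand table of Section 11.4.3.1, a patient who starts corticosteroids is a non-responder, with the remark "Note: the composite strategy will be considered if a patient receives rescue medication any time during the study".

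**Part C conduct.** Section 8.10.1 lists among the prohibited drugs "Swallowed topical corticosteroids (may be used as rescue treatment for EoE) (Parts A and B only"), and limits systemic corticosteroids in the same way. Section 8.3 lets rescued patients continue study drug. It leaves a biopsy before Part C rescue to the investigator and adds that "future endoscopies/biopsies (week 100 and week 160) would still be required". Section 6.1 agrees: the pre-rescue biopsy "only applies to rescue medication and/or procedures that occur before the week 52 visit".

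**Part C endpoint and analysis.** Section 4.1.2 lists "Proportion of patients achieving peak esophageal intraepithelial eosinophil count of ≤6 eos/hpf (400×) at week 100 and week 160", with a parallel endpoint at below 15 eos/hpf. Neither carries a condition on rescue. Section 11.4.3.2 says "Efficacy data in Part C will be summarized with descriptive statistics for treatment received in Part C", and also by Part A and Part B group. The Part B paragraph says "No missing values will be imputed", and the Part C paragraph repeats this. Section 2.2 makes efficacy of dupilumab over up to 160 weeks a secondary objective.

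**The concern.** The Introduction reports that swallowed topical corticosteroids can induce histologic remission. A low eosinophil count in a child taking dupilumab and rescue steroids therefore cannot be credited to dupilumab alone. At week 16 the protocol deals with this by counting rescue as failure. At weeks 100 and 160 it does not, although steroids are then freer and the biopsy after rescue is mandatory.

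What is at stake is the meaning of a secondary, uncontrolled response rate reported as long-term dupilumab efficacy. With no control arm after week 16, nothing in the data would show how much of that rate came from rescue.

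There is also a practical side. Two footnotes to the schedule of events do not match Section 8.3 on which biopsies follow rescue, and those footnotes instruct sites directly.

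**Working it through.** **1. Does any rescue rule reach Part C?**

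| Rule | Where it stands | Reaches Part C? |
|---|---|---|
| Rescue is treatment failure | 8.3, for Part A efficacy analyses | No |
| Composite strategy (non-responder) | 11.4.3.1, row for the week-16 primary endpoint | No |
| Data after rescue set to missing | 11.4.3.2, under the week-16 (Part A) heading | No |
| Tests done as described above | 11.4.3.2, Part B paragraph; concerns optional tests | No |
| Part C paragraph | 11.4.3.2; descriptive, no imputation | No rescue rule stated |

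The remark about rescue at any time during the study belongs to an endpoint measured at week 16, so it cannot define response at week 100.

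**2. Following one child.** A child in Part C starts swallowed steroids as rescue. This is permitted (8.10.1). Dupilumab continues (8.3). No biopsy is needed first (6.1, 8.3), and the week-100 biopsy is still due (8.3). If it shows at most 6 eos/hpf, the child meets the endpoint in 4.1.2, and nothing in 11.4.3.2 removes the child.

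**3. Size.** The protocol gives no Part C rescue rate and no remission rate on steroids, so there is no stated figure to reproduce. Let n be the children biopsied at the visit, x those at or below 6 eos/hpf, and k those among x who were rescued earlier in Part C. If every rescued child has a biopsy, the observed rate is x/n, the rate with rescue as non-response is (x − k)/n, and the gap is k/n. In percentage points:

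| n | k = 1 | k = 2 | k = 3 |
|---|---|---|---|
| 90 (all planned children enter Part C and are biopsied) | 1.1 | 2.2 | 3.3 |
| 30 (one full Part A arm) | 3.3 | 6.7 | 10.0 |
| 20 (assumed number left in an arm) | 5.0 | 10.0 | 15.0 |

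Equivalently, the gap is (share rescued) × (share of those at or below 6 eos/hpf). Assuming 5–20% rescued and 30–70% of them in remission:
- 0.05 × 0.30 = 1.5 points
- 0.10 × 0.50 = 5.0 points
- 0.20 × 0.70 = 14.0 points

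These are illustrations. At k = 0 the gap is zero.

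**4. Which denominator should a supportive rate use?** Children leave Part C by design: when dupilumab becomes commercially available in their country (6.1), or, where it is already marketed for patients aged 12 and over, on reaching the age and weight limit (8.1). Suppose 20 of 30 remain and 12 respond. The observed rate is 12/20 = 60%. Dividing by all treated children gives 12/30 = 40%, a loss of 20 points from administrative exit alone, against 5.0 points for one rescued responder. The better denominator is n + m, where m is the number of rescued children without a biopsy at that visit. With x = 12, n = 20, k = 1 and m = 1, the supportive rate is (12 − 1)/(20 + 1) = 11/21 = 52.4%.

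**5. Footnotes against Section 8.3.**
- Table 3 footnote 4a cancels the week-100 and week-160 biopsies, among others, for a patient biopsied before rescue. Section 8.3 requires them after Part C rescue. The two conflict.
- Table 2 footnote 7a cancels the biopsies at weeks 16 and 52. Section 8.3 assigns them respectively to rescue in Part A and Part B. A child rescued in Part A after a biopsy is not barred from Part B (7.2.2.2). Section 8.3 keeps that child's week-52 biopsy; footnote 7a can be read as cancelling it. Table 1 footnote 2b, worded with and/or, does not settle the matter.

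**The case against.** No sentence says that a remission after rescue counts. Section 11 only provides the basis for the SAP, which is not at hand and could add a rule. Part C was added mainly for long-term safety and relaxes background care generally: PPI use may be adjusted, the diet restrictions cover Parts A and B, and food re-introduction is itself an endpoint. Reporting histology as observed is a legitimate treatment-policy summary. Everything after Part A is descriptive.

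Much of this stands. It is why the observed rate should stay and why the severity is low. It does not remove the point: the protocol expressly limits the failure rule to Part A and then sets Part C conditions under which post-rescue remissions are produced and biopsied. The SAP can repair the analysis, but it cannot correct site instructions in the schedule footnotes.

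On the footnotes, 7a is attached to both the week-16 and week-52 endoscopies and can be read distributively, in agreement with 8.3. Footnote 4a marks only the early-termination columns, so its practical effect is small. If it were followed, a child biopsied before rescue would have no later biopsy to count, which would narrow the problem.

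A reader might infer that the week-52 rate is inflated in the same way. The documents do not support that. A child rescued in Part B is biopsied beforehand and skips the scheduled week-52 biopsy, and the analysis set in 11.3.3 is every child who received a dose. Whether such a child drops out of the rate depends on a denominator that the protocol does not fix.

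**Conclusion.** The point holds for Part C, at low severity. As written, a count at or below 6 (or below 15) eos/hpf on rescue steroids enters the descriptive long-term dupilumab rate at weeks 100 and 160. The gap is k/n, of unknown total size and zero without rescue. This rests on reading the protocol as it stands, with no further rule in the SAP.

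Two stronger conclusions might be drawn and should not be. First, the primary result, alpha and power are unaffected: the week-16 endpoint has its own rescue rule, and Parts B and C carry no formal hypothesis. Second, counting rescue as failure would not make the long-term rates comparable with week 16. Lower-exposure children move to the higher exposure, dosing tiers change, PPI and diet may change, and some children re-enter after an end-of-study visit. The added summary answers one narrower question: how much of the observed rate depends on rescued children.

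**What to change.** **Analysis.** In the Part C paragraph of Section 11.4.3.2, keep the as-observed rates and add a supportive summary of the binary histology endpoints at weeks 100 and 160:
- A child rescued during Part C before the assessment (systemic or swallowed corticosteroids, or dilation) is a non-responder.
- The denominator is the children with a biopsy at that visit plus rescued children without one.
- Children who left by design before the visit (commercial availability, or the age and weight limit) and without rescue are not counted as failures.
- All treated children are not used as the denominator at these visits.

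A rescued child's outcome here is fixed by the rescue itself, so the statement against imputing missing values can stay.

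**Schedule.** Remove weeks 100 and 160 from Table 3 footnote 4a. Reword Table 2 footnote 7a so that rescue skips only the biopsy of the part in which it occurred; a child rescued in Part A who enters Part B then keeps the week-52 biopsy.

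**Cost.** A few descriptive tables and two footnote edits, with no endoscopy beyond those Section 8.3 already requires. The supportive rate cannot exceed the observed one, and a short steroid course long before the visit still counts as failure in it, which is a further reason to show both.

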# 8.4. Dose Modification and Study Treatment Discontinuation Rules

## 8.4.1. Dose Modification

Dose Modification, beyond what is specified by the protocol on dose regimen changes based on weight changes (see below), is not allowed.

Since dose is weight-tiered, weight at baseline will be used to determine dose for the 16-week double-blinded treatment period, weight at visit 8 (week 16) will be used to determine dose for start of the 36-week extended active treatment period and weight at Visit 17 / week 52 (or start of open-label period) will be used to determine the dose for the open-label extension period. All patients (Part C) will receive higher exposure dupilumab regimens based on body weight at visit 17 (week 52, end of extended active treatment period) or start of open-label period (for re-entry patients). Dose adjustments (based on increased weight) will be made during Part C at specified in-clinic visits as indicated in Table 4.

## 8.4.2. Study Drug Discontinuation

Patients who permanently discontinue from study drug should be encouraged to remain in the study. Those who agree and do not withdraw from the study will be asked to return to the clinic for all remaining study visits per the visit schedule.

Patients who permanently discontinue from study drug and who opt to withdraw from the study will be asked to complete study assessments, per Section 9.1.2.

#### 8.4.2.1. Reasons for Permanent Discontinuation of Study Drug

Study drug dosing will be permanently stopped in the event of:

- Evidence of pregnancy
- Serious or severe allergic reactions considered related to study drug
- Specific types of liver dysfunction [eg, Hy's law is met (Malmberg, 2009)]
- Patient or legal parent/legal guardian withdraws assent or consent
- Anaphylactic reaction or other severe systemic reaction deemed related to study drug
- Diagnosis of a malignancy during study
- Any infection that is opportunistic, such as TB and other infections whose nature or course may suggest an immunocompromised status

Regeneron Pharmaceuticals, Inc.

